Increased Lung Volume as Rescue Therapy for Asthma

NCT02696980

3/5/2018

Human Subjects Research Protocol

The Common Human Subjects Protocol Cover Form **must** be completed and **attached** to the front of this form. This Protocol form should be completed for any human subjects research proposal that does not have a specific "protocol," such as a grant application. This form must be submitted along with a copy of the complete grant proposal and all the information in this form **must** be consistent with that proposal. This protocol form, once IRB approved, will be the working protocol for that research. **When completing this document, do not refer to page numbers within your grant.** If revisions are necessary during the course of the research, amendments should refer to this protocol form, not the grant proposal. Enter responses for all sections. Check N/A if the section does not apply.

PROTOCOL SUMMARY

Project Title:

Protocol Version Date:

Increased Lung Volume as Rescue Therapy for Asthma

05 March 2018

Principal Investigator:

[name]

Grant Sponsor:

NIH

Grant Number:

R01HL130847-01

(For grants routed through UVM, indicate the OSP Proposal ID # located at the top of the OSP Routing Form)

Lay Language Summary: (Please use non-technical language that would be understood by nonscientific IRB members to summarize the proposed research project. The information must include: (1) a brief statement of the problem and related theory supporting the intent of the study, and (2) a brief but specific description of the procedure(s) involving the human subjects. Please do not exceed one single-spaced 8 1/2 X 11" page.)

The purpose of this study is to test the effect of increasing lung volume with a simple hand-held device to both prevent, and also to relieve, airway constriction in people with asthma and a BMI ≥ 30 kg/m².

We will recruit 20 people who have late onset non-allergic asthma and a BMI of ≥ 30 kg/m². We will test the efficacy of elevating lung volume on both preventing and reversing bronchoconstriction in these people. We will elevate lung volume by having patients breathe out against a small level of resistance.

The ultimate purpose of this research is to develop a new treatment for asthma that occurs in the setting of obesity.

PURPOSE AND OBJECTIVES

Purpose: The importance of the research and the potential knowledge to be gained should be explained in detail. Give background information.

We propose a study to investigate whether PEEP can prevent and/or reverse bronchoconstriction in obese asthmatics.

Obesity is a major risk factor for the development of asthma, with about 250 000 new cases of asthma in the United States per year related to the obesity epidemic.¹ Not only is obesity a risk factor for the development of asthma, but these patients tend to have more severe disease (with a nearly 5-fold risk of hospitalization); a recent survey study found that more than 50% of severe asthmatics in the U.S. are obese.²⁻⁵ Our group has contributed to major advances in the understanding of this disease.⁶⁻⁸ We have found a novel form of asthma: late-onset non-allergic disease that develops consequent to obesity. Understanding the pathogenesis of airway disease in this late-onset non-allergic group is the focus of the current proposal. There is a critical need to understand this form of disease as obese patients do not respond as well to conventional asthma medications,^{4,5,9} likely because all treatments for asthma have

been developed to treat early-onset allergic disease in lean patients. **There is a critical need to understand the pathophysiology of airway disease in late-onset, non-allergic obese asthmatics, in order to develop therapies to target this disease.**

Airway hyperresponsiveness (AHR) is a defining characteristic in asthma. In early-onset allergic asthma, AHR is caused by lymphocyte-driven allergic inflammation which leads to remodeling in the airway and causes hyperresponsiveness of airway smooth muscle; airway narrowing results from constriction of smooth muscle, inflammatory thickening of the airway wall, and secretion of mucus and inflammatory mediators into the airway lumen. In stark contrast, we have found minimal inflammation in obese late-onset asthmatics.⁷ Indeed, lung function tests are more suggestive of distal airway closure rather than airway narrowing as a cause of hyperresponsiveness in these patients (see preliminary data and our recent publication in *Respirology*¹⁰). We have also found that obese individuals who develop this late-onset non-allergic asthma tend to have more collapsible lung peripheries than obese individuals who do not develop asthma.⁸ This closure manifests largely in the small airways because their narrow lumens are particularly susceptible to occlusion by mucus plugs compared to larger airways (although closure can potentially occur anywhere throughout the airway tree).

- A) We will ask participants to return for 2 visits in which we will administer methacholine concurrently with varying levels of PEEP (using PEEP to prevent bronchoconstriction).
- B) Subject will return for another 2 visits in which we will determine the effects of PEEP subsequent to methacholine challenge (using PEEP to reverse bronchoconstriction).

The reason to test both short-term time points is to assess:

- A) whether PEEP has any value as an intervention that will prevent the immediate development of bronchoconstriction (i.e. bronchoprotection, analogous to using rescue therapy prior to exercise to prevent bronchoconstriction), and
- B) if PEEP will reverse established bronchoconstriction (i.e. bronchodilation, as a form of rescue therapy after onset of symptoms).

These studies will be completed over 5 visits. If necessary, participants may be asked to return for an additional visit if some of the lung function tests were not completed at the regularly scheduled visits, if the lung function testing was completed, but did not produce consistent and accurate results, or if there is a longer than expected gap between study visits, which creates a need to calculate a new PC₂₀ dose for the participant through an additional methacholine challenge.

Procedures: Describe all procedures (sequentially) to which human participants will be subjected. Identify all procedures that are considered experimental and/or procedures performed exclusively for research purposes. Describe the types, frequency and duration of tests, study visits, interviews, questionnaires, etc. Include required screening procedures performed before enrollment and while on study. Please provide in table, list or outline format for ease of review. (describe and attach all instruments)

Note: A clinical research protocol may involve interventions that are strictly experimental or it may involve some aspect of research (e.g., randomization among standard treatments for collection and analysis of routine clinical data for research purposes). It is important for this section to distinguish between interventions that are experimental and/or carried out for research purposes versus those procedures that are considered standard therapy. In addition, routine procedures performed solely for research purposes (e.g., additional diagnostic/follow-up tests) should be identified.

All procedures will be performed exclusively for research purposes.

- Baseline Medical History: we will obtain a baseline medical history and record all medications
- Baseline anthropometrics (BMI, waist and hip circumference, as well as temperature and blood pressure)
- Asthma Questionnaires: participants will complete a validated questionnaire to assess asthma control.¹⁶
- Berlin Sleep Questionnaire (modified version)
- Blood draw: We will draw 10 cc of blood; this will go to the UVMMLC laboratory for measurement of complete blood count and differential, and IgE levels (these are used as measures of allergic status). IgE will not be repeated if tested previously.

- Blood draw: We will draw 16cc of blood, this will go to [name] UVM laboratory for measurement of serum biomarkers (used to detect circulating anti-inflammatory markers)
 - Subjects consenting to store leftover blood samples and data for future research on asthma and obesity will have sample stored in a bio-repository under CHRMS: 16-636.
- Spirometry without bronchodilator will be performed per standard clinical protocol.
- Urine pregnancy test will be performed at all visits.
- Lung Volumes will be measured per standard clinical protocol (by plethysmography).
- Methacholine challenge test (conventional): this will be performed per standard clinical protocol. Participants will inhale increasing doses of methacholine to identify the concentration of methacholine producing a 20% decrease in FEV₁ or FVC (the PC₂₀ dose); this concentration will be used in the subsequent single dose methacholine challenge testing.
- Chest CT: A chest CT will be performed with images at different lung volumes, and with PEEP at a setting of 10 cmH₂O, to assess changes in airway diameter during breathing (if participant has not had this performed previously as part of protocol 15-327 or protocol 16-061).
- Single breath nitrogen wash out: the participant will take a single deep breath of 100% oxygen, and then exhale through a one way valve. (if participant has not had this performed previously as part of protocol 15-327 or protocol 16-061).
- Multiple breath nitrogen wash out: the participants will breathe 100% oxygen for approximately 7 minutes (normal tidal breathing). (if participant has not had this performed previously as part of protocol 15-327 or protocol 16-061).
- Single dose methacholine challenge test at PEEP 0 or PEEP 10 with forced oscillation: The experimental protocol will consist of having the subject breathe a fixed concentration of methacholine aerosol for four and a half minutes; we will use the dose of methacholine that produces a 20% fall in FEV₁. We will measure airway impedance by the forced oscillation technique before, during and after the inhalation of methacholine. Subjects breathe, taking normal breaths, through a conventional plastic mouthpiece attached to a specialized apparatus that measures respiratory impedance by pressure changes related to a variable airflow during normal breathing.

Study Visits:

	Visit 1	Visit 2	Visit 3	Visit 4	Visit 5
Baseline history	*				
IgE level / CBC with differential	*				
Serum Biomarker	*				
Pregnancy Test ¹	*	*	*	*	*
Asthma Control Questionnaire	*	*	*	*	*
Berlin Sleep Questionnaire	*				
Conventional methacholine	*				
Lung Volumes	*				
SBNW ²	*				
MBNW ²	*				
Training for CT breathing ²	*	*			
CT imaging ^{2,3}		*			
PEEP + methacholine together		*	*		

Methacholine prior to PEEP				*	*
PEEP level (cmH ₂ O)		0	10	0	10

¹For women of child-bearing potential

²Participants who have not previously completed these procedures as part of a related research protocol only.

³ CT imaging may be performed at any of visits 2-5, at convenience of participant

Study Visits:

There will be five regularly scheduled study visits, with some participants asked to complete a screening visit, as follows:

*Screening Visit: Participants who have not had a serum IgE level drawn/results are not available will be asked to attend a screening visit. The research staff will provide participants with full details of the study. Participants who sign a consent form will have blood drawn for measurement of IgE and Complete blood count with differential (assesses allergy, and required for eligibility assessment), and for serum anti-inflammatory biomarkers. In addition, the eligibility criteria for the study will be reviewed with the participants, which may involve a height and weight measured to test for BMI eligibility.

Visit 1: This visit will take approximately 3 hours. The research staff will provide participants with full details of the study. Participants who sign a consent form will undergo the following procedures/ assessments. Past medical history, asthma control questionnaire, Berlin Sleep Questionnaire, urine pregnancy test, measurement of height, weight, blood pressure, waist and hip circumference, as well as temperature. Eligible participants will undergo spirometry and lung volumes measurements. Participants who have not previously had the following tests will undergo a single-breath (SBNW) and multi-breath (MBNW) nitrogen (N₂) washout methods to assess functional residual capacity (FRC), closing volume, closing capacity, lung clearance index (number of FRC turnovers required to reduce N₂ concentration to 1/40 of its initial value), and lung heterogeneity (reflected in the washout parameters Sacin and Scond).

Participants will undergo a standard methacholine challenge for measurement of PC₂₀, a standard measurement of airway reactivity. Using the medical records we will screen for methacholine challenge results performed in the past two weeks.

Participants will also have blood drawn at visit 1, which will go to [name] UVM laboratory for measurement of serum biomarkers. If this blood draw cannot happen at visit 1 for logistical reasons, then it may be performed at visits 2-5.

Visits 2-5 will be conducted in random order using a schema provided by the biometry facility at the University of Vermont.

Visits 2 & 3: Participants will be questioned about their interim history to asses for adverse events and will be asked to complete the asthma control questionnaire. In addition, participants will undergo a methcholine challenge, while we continuously measure their lung function by forced oscillation.

We will administer a single dose of methacholine (as determined by their PC₂₀ dose, the dose of methacholine required to produce a 20% decreased in FEV1), and measure respiratory system impedance with the forced oscillation system while concurrently applying either PEEP 0 or PEEP 10.

Visit 4 & 5: Participants will be questioned about their interim history to assess for adverse events, and will be asked to complete the asthma control questionnaire. In addition, participants will undergo a methcholine challenge, while we continuously measure their lung function by forced oscillation.

We will administer a single dose of methacholine (as determined by their PC₂₀ dose, the dose of methacholine required to produce a 20% decreased in FEV1), and measure respiratory system impedance with the forced oscillation system, *after* the single dose of methacholine, we will apply either PEEP 0 or PEEP 10.

Participants who have not had a chest CT as part of protocol 15-327 will undergo a protocolized non-contrast chest CT. Images will be taken at full inspiration, resting expiration (FRC), full expiration (residual volume), and resting expiration with PEEP10cmH₂O. Images will be recorded using standardized procedures, and analyzed using commercially available software for quantification of airway diameter, airway thickness, and lung attenuation at standardized locations in both lung fields. These measurements will allow us to directly quantify changes in the large airways (diameter and wall thickness), and also airway trapping (degree of attenuation) through the normal respiratory cycle.

Additional Visit: Some participants may be asked to return for an additional visit if some of the lung function tests were not completed at the regularly scheduled visits, if the lung function testing was completed, but did not produce consistent and accurate results, or if there is a longer than expected gap between study visits, which creates the need to calculate a new PC₂₀ dose with an additional methacholine challenge.

This additional visit may involve spirometry, lung volume measurements, single-breath nitrogen washout, multiple-breath nitrogen washout, a methacholine challenge, or the forced oscillation procedure with a single dose of methacholine, depending on the need for the specific participant.

If methacholine is needed during the additional visit, the participant’s blood pressure will be assessed. In addition, women of childbearing potential will be required to undergo a urine pregnancy test prior to methacholine testing.

For research involving survey, questionnaires, etc.: Describe the setting and the mode of administering the instrument and the provisions for maintaining privacy and confidentiality. Include the duration, intervals of administration, and overall length of participation. (describe and attach all instruments)

Not applicable

Baseline medical and asthma control questionnaires will take 5- 10 minutes to complete, will be completed at the Medical Office Building, in a private office. Questionnaires are in paper format, and will be completed by the participant.

Statistical Considerations: Delineate the precise outcomes to be measured and analyzed. Describe how these results will be measured and statistically analyzed. Delineate methods used to estimate the required number of subjects. Describe power calculations if the study involves comparisons. Perform this analysis on each of the primary and secondary objectives, if possible.

We will compare changes in respiratory system impedance across the 2 levels of PEEP for participants being exposed to methacholine prior to PEEP (visit 4-5) and methacholine simultaneously with PEEP (visits 2-3), separately.

We will also measure symptom scores using the Borg scale; symptom scores in the obese are related to lung reactance, and we anticipate that symptom scores will be decreased by the PEEP intervention and that this will correlate with decreases in measures of impedance.

The primary statistical analysis will be to compare changes in measures of impedance at PEEP 0 versus 10 cmH₂O using paired t-tests. If normal distribution assumptions are not met, variables will be appropriately transformed. We will compare data from visits 2-3, and visits 4-5 as separate experiments, as they address different scientific questions. We will also compare symptom scores (Borg scale) and, FRC at the two different levels of PEEP.

Power Analysis: Based on the preliminary data shown in Figs. 10 & 11 obtained with a PEEP of 10 cmH₂O, we anticipate that a PEEP of 10 cmH₂O will lead to a 50% attenuation in the increase in resistance in response to methacholine compared to the increase in resistance at PEEP 0, which will be our primary outcome of interest. From our prior work using a commercially available forced oscillation system in obese asthmatics,

we anticipate that the baseline resistance of the respiratory system at a frequency of 5 Hz will be 7.02 ± 1.80 cmH₂O.s/L, and that this will increase to 10.50 ± 2.20 cmH₂O.s/L with a PC₁₀ dose of methacholine at PEEP = 0. Examination of the change in resistance in response to methacholine for PEEP = 0 compared to PEEP = 10 using a paired t-test with a 2.5% Type I error level and $r = 0.50$ within subject correlation indicates that a sample size of $n = 10$ LONA subjects will provide 99% power to detect the postulated within subject change. An independent comparison using a 2.5% Type I error level for the change in resistance prior to methacholine using the smaller effect sizes would require a sample size of $n = 15$ to achieve a 78% power. An adjusted 5% Type I error level was used to compensate for the two separate comparisons conducted for testing the resistance changes. We will increase this to 20 participants to allow for potential drop-outs and any technical difficulties participants experience with completing any of the study visits.

Confidentiality Measures and Secure Storage of Data or Tissue: Describe how the data/tissue will be collected. Will there be identifiers or will the data/tissue be coded? Describe where the data/tissue will be stored and how it will be secured. Describe who will have access to the data/tissue or the codes. If subject data/tissues with identifiers will be released, specify to whom. Describe what will happen to the data/tissues when the research has been completed.

Not Applicable

- Research material obtained from participants will include results of lung function testing, and medical history obtained from direct patient interview.
- People having access to protected data will be the investigators participating in this study and appropriate regulatory authorities.
- Documents containing identifiable information will be kept in a locked file cabinet at the Vermont Lung Center. All participants will be assigned a unique study ID, which be kept in this locked file cabinet. Study specimens will be labeled with the study ID, and not identifiable information. Our study database will be password protected, and participants will be identified in the database only by their unique participants ID.
- Optional Leftover blood samples and data for future research on asthma and obesity will be stored frozen in [name] UVM laboratory bio-repository (CHRMS: 16-636). The samples will be identified with the unique study ID and date only.

Risks/Benefits: Describe any potential or known risks. This includes physical, psychological, social, legal or other risks. Estimate the probability that given risk may occur, its severity and potential reversibility. If the study involves a placebo or washout period, the risks related to these must be addressed in both the protocol and consent. Describe the planned procedures for protecting against or minimizing potential risks and assess their likely effectiveness. Where appropriate, discuss plans for ensuring necessary medical or professional intervention in the event of adverse effects to the subjects. Discuss the potential benefits of the research to the subjects and others. Discuss why the risks to the subjects are reasonable in relation to the anticipated benefits to subjects and others. Discuss the importance of the knowledge gained or to be gained as a result of the proposed research and why the risks are reasonable in relation to the knowledge that reasonably may result. If there are no benefits state so.

Risks

Lung Function tests (spirometry and lung volumes, and single breath and multiple breath wash out tests):

These tests involve taking a very deep breath and breathing out fast, the main risk of this is that it can be tiring. We will give the patients as much time as they need to complete this testing.

Standard Methacholine challenge:

This test involves the inhalation of an agonist to induce bronchoconstriction and may induce the symptoms of an asthma exacerbation (chest tightness, dyspnea, coughing). The procedure is performed in a closely monitored clinical environment, with availability of bronchodilator. This procedure has been safely used in many previous studies in our division and nationwide, we will only perform this procedure if the baseline FEV₁ is > 60% predicted.

Bronchodilator (albuterol/salbuterol):

This medication will be available to be administered only if the participant is uncomfortable from the effects of the methacholine challenge test. These drugs can lead to tremor, nervousness, tachycardia, palpitations

and headache – these reactions are transient and rare (<5%) with the proposed doses used for this study, and if they occur, we will monitor the patient until they return to baseline. High doses may cause arrhythmias and hypokalemia: these are very unlikely with the doses used for this study.

Modified Methacholine with Flexivent.

Some subjects may feel discomfort from the slight oscillation of air in their mouth while they breathe, we will minimize this by using the dose of methacholine required to produce a 20% fall in FEV₁. We will perform this test with positive airway pressure at visit 3. The positive airway pressure is likely to be well tolerated, similar levels are conventionally used in the treatment of sleep apnea.

Chest CT

Computed tomography (CT scan): This is a routine imaging procedure used in pulmonary medicine. We plan to perform limited scans of your lungs. The scan results in a radiation dose of up to 3.0 mSv. This is equivalent to the exposure from natural background radiation in our surroundings over 6 months.

For comparison, the maximal permissible whole-body occupational radiation dose set by the federal government for people who work with radiation or volunteer for medical research is 50 mSv per year.

Abnormality detected during study procedures: if we detect an unexpected abnormality on the chest CT, or in the participant’s lung function testing, we will communicate this with the participant, and with their permission, the participant’s physician. If the participant has no regular physician, we will help them schedule an appointment with an appropriate health care provider.

Venipuncture (Blood Draw): We will collect a total of 26cc of blood for analysis of IgE and a complete blood count (10cc) as markers of allergic inflammation, and (16cc) serum for circulating anti-inflammatory bio-markers.

Confidentiality

The study also includes a risk of loss of confidentiality. We will follow Health Insurance Portability and Accountability Act guidelines on confidentiality and minimize these risks by assigning unique identifiers to health information, maintaining all records in a locked storage area, and using password protected electronic devices.

Potential Benefits of the Proposed Research to the Subject and Others

There are no direct benefits to patients from participating in this trial other than accurate diagnostic evaluation of any airway disease.

Importance of Knowledge to be gained

The benefit to others is to increase our understanding of the link between asthma and obesity, and potentially identify therapeutic strategies for treating asthma associated with obesity – two diseases which are at epidemic levels in the United States.

***Therapeutic Alternatives:** List the therapeutic alternatives that are reasonably available that may be of benefit to the potential subject and include in the consent form as well.*

Not Applicable

***Data Safety and Monitoring:** The specific design of a Data and Safety Monitoring Plan (DSMP) for a protocol may vary extensively depending on the potential risks, size, and complexity of the research study. For a minimal risk study, a DSMP could be as simple as a description of the Principal Investigator’s plan for monitoring the data and performance of safety reviews or it could be as complex as the initiation of an external, independent Data Safety and Monitoring Board (DSMB). The UVM/UVM Medical Center process for review of adverse events should be included in the DSMP.*

Three physician scientists who are active in asthma research outside of Vermont will participate in a Data

Safety Monitoring Panel (DSMP). The panel will convene annually, primarily to review safety, and also to review the integrity of the data, and will provide recommendations regarding continuation of the studies.

During the study period if there is a primary reason to halt this study related to concerns regarding safety we will stop the protocol in the event of the following.

1. Serious Adverse Events:

The protocol will be stopped for any serious adverse event that is definitely or probably related to the study protocol. The protocol will be stopped in the event that there are two events that are thought to be possibly related to the study protocol.

2. Adverse Events:

For adverse events that are not within the category of serious adverse events, the protocol will be stopped in the events that are 3 adverse event of grade 3 category that are thought to be definitely or probably related to the study protocol. The study will not be stopped for grade 2 or lower adverse events.

Stopping Rules for an Individual Participant/Cohort

A study participant will be discontinued from the study for:

- Any clinical adverse event, laboratory abnormality, intercurrent illness, other medical condition or situation occurs such that continued participation in the study would not be in the best interest of the participant.
- Development of any exclusion criteria may be cause for discontinuation.

Composition of the DSMP

Chair:

[name]
 Garnjobst Chair, Department of Medical Education
 Portland Providence Medical Center
 [name]
 [name]
 [name]
 [contact]

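### Prevention experiment (visits 2-3): methacholine is inhaled by free breathing for a fixed time while PEEP is applied, so the inhaled amount can differ by PEEP level and the paired t-test would credit that difference to PEEP

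*Combined protocol and SAP*

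**What the plan says.** The conventional challenge at visit 1 yields a PC₂₀ concentration, and the Procedures section states that "this concentration will be used in the subsequent single dose methacholine challenge testing". The bullet on the single-dose test then describes "having the subject breathe a fixed concentration of methacholine aerosol for four and a half minutes". On breathing it says only: "Subjects breathe, taking normal breaths, through a conventional plastic mouthpiece". No respiratory rate, tidal volume or minute ventilation is set, and no inhaled or delivered amount is measured.

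The two experiments differ in when PEEP is applied. Under Study Visits, Visits 2 & 3, staff give the methacholine and "measure respiratory system impedance with the forced oscillation system while concurrently applying either PEEP 0 or PEEP 10". Under Visit 4 & 5, PEEP comes afterwards: following "the single dose of methacholine, we will apply either PEEP 0 or PEEP 10". The Lay Language Summary says that lung volume is raised by exhaling against a resistance. Visits 2-5 run in random order.

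Under Statistical Considerations: "The primary statistical analysis will be to compare changes in measures of impedance at PEEP 0 versus 10" cmH₂O, by paired t-tests, with visits 2-3 and visits 4-5 analysed as separate experiments. Borg scores and FRC are also compared between PEEP levels. Neither of these measures dose.

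**The concern.** The protocol calls the challenge a single dose, but what it holds constant is concentration multiplied by time. With free tidal breathing, the amount inhaled also depends on the volume breathed in over the 4.5 minutes. At visits 2-3 the intervention acts on breathing while the stimulus is being delivered.

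The usual protections do not help here. Pairing removes stable differences between people, and random order removes period effects on average. A dose difference produced by PEEP travels with the PEEP level in every participant and every order, so it enters the mean paired difference directly.

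The first objective is whether PEEP prevents the rise in impedance. A weaker stimulus at PEEP 10 would give the same primary result as protection, and a stronger one would mask protection. Visits 4-5 are not exposed in this way, because methacholine is given before PEEP at both levels. A dosing difference confined to visits 2-3 could therefore look like PEEP preventing but not reversing constriction, and readers would take that as physiology.

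**Working it through.** **Inputs (Power Analysis).** Baseline resistance at 5 Hz 7.02 (SD 1.80); after methacholine at PEEP 0, 10.50 (SD 2.20), in cmH₂O.s/L; within-subject correlation 0.50; type I error 2.5%; postulated attenuation 50%; 20 participants. The protocol does not state sidedness; two-sided is assumed.

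**Derived quantities.**
- Rise at PEEP 0: 10.50 − 7.02 = 3.48. Postulated effect: 0.5 × 3.48 = 1.74.
- SD of a change: √(1.80² + 2.20² − 2 × 0.5 × 1.80 × 2.20) = √4.12 = 2.03.
- SD of the difference between two such changes at correlation 0.5: √(2 × 4.12 × 0.5) = 2.03.

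**Reproducing the plan's figures (noncentral t).** With effect 1.74, SD 2.03 and n = 15, power is 78.1%, matching the stated 78%. The stated 99% at n = 10 returns (99.1%) only with the full 3.48 as the effect; with 1.74 it is 53.6%. That is a separate matter, but the match at n = 15 supports SD 2.03 and a two-sided test as the plan's working values.

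**Size of a possible artefact.** The documents give no ventilation figures, so the dose reduction and the dose-response shape are assumptions, shown as ranges. PEEP is assumed to have no true effect. If the inhaled amount at PEEP 10 is lower by a fraction f, the spurious attenuation is 3.48 × f for a rise proportional to dose, and 3.48 × (1 − √(1 − f)) for a square-root response. The last two columns give the chance of a significant result in the protective direction at n = 20.

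| f | Spurious attenuation, proportional | Spurious attenuation, square root | False prevention, proportional | False prevention, square root |
|---|---|---|---|---|
| 10% | 0.35 | 0.18 | 6% | 3% |
| 20% | 0.70 | 0.37 | 21% | 7% |
| 30% | 1.04 | 0.57 | 46% | 14% |

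With equal doses the chance in that direction is 1.25%. At n = 15 the proportional case gives 5/15/34%. As a share of the postulated 1.74, the proportional artefacts are 20/40/60%.

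**Would adjusting for volume settle it?** Regress the paired difference in the resistance rise on the paired difference in inspired volume, and read the intercept as the PEEP effect at equal volume. Assume a between-person SD of 15% for the volume difference and n = 20. Relative to the unadjusted mean, the intercept's standard error is multiplied by √(1 + n·m²/((n − 1)·0.15²)), where m is the mean volume deficit:
- m = 10%: √(1 + 0.20/0.4275) = 1.21
- m = 20%: √(1 + 0.80/0.4275) = 1.69
- m = 30%: √(1 + 1.80/0.4275) = 2.28

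By simulation, the intercept test has power of about 73/44/25% for a true 1.74 effect at those deficits. The plain t-test has 91% when doses are equal. With no true effect the intercept test holds its 2.5% level, but only if volume is unaffected by constriction. If constriction itself changes the volume breathed (3% or 5% more volume per 1 cmH₂O.s/L less constriction, at a 20% mean deficit), simulation has the intercept falsely showing prevention in roughly 18% to 41% of null trials.

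**The case against.** The strongest reply is that nothing in the documents shows a difference in inhaled amount. Both PEEP levels carry the same instruction to breathe normally, which is partial standardisation. The preliminary PEEP 10 figures, cited in the Power Analysis, cannot be seen here. This stands, and it keeps the point conditional. It does not remove the gap, because asking for normal breaths sets no volume and nothing is planned to check it.

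Second, a strictly proportional response lies towards the upper end of plausible sizes. This also stands, which is why the square-root range is given beside it.

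Third, a reader might infer that inspired volume is already in hand, since the protocol describes a "specialized apparatus that measures respiratory impedance by pressure changes related to a variable airflow during normal breathing". The text does not say that the flow trace is stored, or that it captures all inspired flow separately from oscillation and nebuliser flow. That has to be confirmed.

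Fourth, a reader might infer that prevention should be claimed only if a volume-adjusted intercept agrees. The working does not support such a gate: volume is measured after PEEP starts, may respond to constriction, and leaves the intercept imprecise exactly where the concern is greatest. Nor does inspired volume capture aerosol output or deposition.

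**Conclusion.** The point holds as a limit on what the prevention experiment can conclude. The inhaled amount is not fixed by design at visits 2-3, a PEEP-driven difference would pass straight into the primary comparison, and the plan includes nothing that would reveal it. The bias could run either way.

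A reader might go further and infer that PEEP 10 does reduce the methacholine received, so that a positive prevention result would be invalid. The documents do not support this: they contain no ventilation, nebuliser or deposition data under either level. The false-prevention rates are illustrations that depend on the assumed dose reduction and dose-response, on SD 2.03 and on a two-sided 2.5% test.

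One further caution on scale: the 3.48 rise is tied to a PC₁₀ dose in the Power Analysis, whereas the procedures use the PC₂₀. Those passages must be reconciled, and the absolute sizes above would change with the rise and SD that apply. The reversal experiment at visits 4-5 is outside this point.

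**What to change.** Keep the paired t-test as the primary analysis and leave the challenge as it is. Before results are examined, add the following to Statistical Considerations:

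1. Confirm that the forced-oscillation flow signal is stored during inhalation and captures inspired flow. If so, derive total inspired volume over the 4.5 minutes at each of visits 2 and 3.
2. Report the paired difference in that volume (PEEP 10 minus PEEP 0) with a confidence interval, beside the primary result. State in advance what difference will count as material.
3. If the difference is material, say that a difference in delivered methacholine cannot be excluded as an explanation of the prevention result, whichever way that result falls. If the flow signal cannot be used, report the lack of any check on inhaled amount as a limitation.
4. A regression of the paired resistance difference on the paired volume difference may be shown as exploratory, with the intercept's confidence interval. It must not decide whether prevention is claimed.

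The cost is some signal processing and a prevention claim that may have to be qualified. No extra visits or participants are needed. The remaining weakness is that equal inspired volumes would make a dosing explanation less likely without excluding differences in aerosol output or deposition.
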